9.4.2 ANALYSIS OF THE PRIMARY EFFICACY ENDPOINT(S)

The rates of failure of drainage (primary outcome) will be estimated as proportions and compared between the two groups using a Chi-square test corrected for the non-inferiority hypothesis. We will present the findings using the difference in the proportions (rate in small group –rate in large group) and corresponding 95% upper confidence limit.

9.4.3 ANALYSIS OF THE SECONDARY ENDPOINT(S)

Length of stay will be compared using Poisson regression with a main effect of group. Post insertion pain and vital signs will be compared using analysis of covariance controlling for pre-procedural pain and vital signs, respectively, with categorical group effect. We will compare rates of re-intervention and readmission using chi-square tests for independence (or Fisher's exact tests) and present our findings using relative risks and 95% confidence intervals.

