Outcome measures	
Aim I
 
Primary outcome:
 
 • Retained hemothorax requiring an additional intervention, either video-assisted thoracoscopic surgery (VATS) or additional thoracostomy tube placement. 
Secondary outcome:
 
 • Duration of chest tube placement [Time Frame: 90 days] • Length of hospitalization • Subjective pain [Time Frame: 5 minutes pre- and post-insertion], Assessed with 0-10 numeric pain rating scale • Hemodynamic stability post-insertion (determined by vital signs: temperature, heart rate, blood pressure, oxygen saturation) • Initial drainage from chest tube at 5 minutes [Time Frame: 5 minutes] • Tube specific complications: Air leak, tube malposition, & tube migration [Time Frame: 90 days] • Time to radiographic resolution of pneumothorax/hemothorax/hemopneumothorax [Time Frame: 90 days] • Recurrent pneumothorax/hemothorax/hemopneumothorax after tube removal • Readmission for chest tube related complications [Time Frame: 90 days] 
Aim II
 
 • Empyema rates in traumatic pneumothorax, hemothorax, and hemopneumothorax
Description of Study Intervention:	Placement of 14 Fr Thal tube or 28 Fr Chest Tube for Hemopneumothorax.
Study Duration:	2 Years
Randomization	Permuted block randomization with random block sizes to allocate patients in a 1:1 allocation to the 14 or 28 tube sizes. The randomization lists will be generated using SAS Enterprise Guide version 6.1. All study staff collecting and recording data for the trial will be masked to the tube size that was used during the procedure.

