3 OBJECTIVES AND ENDPOINTS

OBJECTIVES	ENDPOINTS
	Primary
Aim I: Determine the safety and efficacy non-inferiority between small bore (14 Fr) and large bore (28 Fr) in the drainage of traumatic hemothorax and hemopneumothorax	Endpoint I: Retained hemothorax requiring an additional intervention, either video-assisted thoracoscopic surgery (VATS) or additional thoracostomy tube placement.
	Secondary
	Endpoint II: Duration of chest tube placement
	Endpoint III: Initial drainage from chest tube at 5 minutes
	Endpoint IV: Length of hospitalization
	Endpoint V: Subjective pain score (pre- and post-insertion recorded within 5 minutes of insertion). Assessed with 0 -10 numerical pain scale
	Endpoint VI: Hemodynamic stability post-insertion (determined by vital signs: temperature, heart rate, blood pressure, oxygen saturation)
	Endpoint VII: Time to radiographic resolution of pneumothorax, hemothorax, hemopneumothorax
	Endpoint VIII: Tube specific complications: Air leak, tube malposition, & tube migration
	Endpoint IX: Recurrent pneumothorax/hemothorax/hemopneumothorax after tube removal
	Endpoint X: Readmission to hospital for a chest tube related complication

OBJECTIVES	ENDPOINTS
Aim II: Determine the incidence of empyema in the setting of traumatic pneumothorax, hemothorax, and hemopneumothorax with the addition of maximum barrier precautions	Endpoint Ia: Empyema rate

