4 STUDY DESIGN

4.1 OVERALL DESIGN

The proposed study is a single center, prospective, non-inferiority trial evaluating the efficacy of small bore (14 Fr) vs large bore thoracostomy tubes in the setting of trauma at an American College of Surgeons designated Level I trauma center. Each patient will receive a study approved thoracostomy tube as indicated and our standard of care thoracostomy tube Practice Guideline will be followed. The study period is from the time of enrollment (visit day 0) up to 90 days (± 14 days) following the date of thoracostomy tube placement. A total of 645 subjects will be prospectively enrolled.

Aim I will be achieved through a prospective randomized study design which will evaluate thoracostomy tubes placed in the setting of traumatic hemothorax or hemopneumothorax. The efficacy of the thoracostomy tube sizes will be determined by assessing the participants for retained hemothorax which will be defined in this study as any residual blood that cannot be drained after 72 hours of thoracostomy as confirmed by imaging. A total of 252 subjects will be enrolled and randomized in this study group.

Aim II will be achieved through a prospective non-randomized controlled study design in which maximum barrier precautions will be used during chest tube placement for all prospective subjects diagnosed with a traumatic pneumothorax, hemothorax or hemopneumothorax. The prospective subjects will be compared to subjects in a retrospective analysis in which the use of maximum barrier precautions was not standard. Maximal barrier precautions will consist of a thyroid drape, hand hygiene, sterile gown, mask, and gloves. The use of sterile technique will be consistent throughout the prospective study. This will limit the variability between the two treatment arms and allow a more accurate comparison of empyema rates between tube size and sterile technique. The use of prophylactic antimicrobial agents will also be collected for these subjects. A total of 645 subjects will be enrolled in this study group (inclusive of those patients enrolled as part of Aim I).

All participants will be monitored for their need for operative intervention (e.g. VATS), development of empyema, hospital readmission, tube related complications (e.g. tube misplacement, tube migration), and death which occurs between thoracostomy tube placement and follow-up.

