6.4 MEASURES TO MINIMIZE BIAS: RANDOMIZATION AND BLINDING

We will use stratified permuted block randomization with random block sizes to allocate patients in a 1:1 allocation to the 14 or 28 tube sizes. The randomization lists will be generated by a study statistician using SAS Enterprise Guide version 6.1 and stratified by location (Emergency Department and Surgical & Trauma ICU). Randomization lists will be provided to the study coordinator and another study team member not affiliated with clinical care and assessments to place the allocations into number opaque envelopes. These envelopes will be pulled sequentially by the surgeon or study team as a patient is deemed provisionally eligible for the study preserving allocation concealment. The ID of the envelope is recorded in the patient's research record.

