9.2 SAMPLE SIZE DETERMINATION

Aim I

This study is a non-inferiority randomized controlled trial comparing placement of 14 French vs. 28 French chest tubes for hemothorax and hemopneumothorax. We hypothesize the rate of drainage failure to be approximately 7% in the large 28 tube size group. With a sample size of n=126 per group, we will have 80% power to detect a non-inferiority margin difference between the group rates of 8% (allowing up to a 15% rate of drainage failure in the small 14 tube size group; $\alpha=0.05$). In our prior study, we saw a 20% vs 6.7% difference in needing additional procedures for pneumothorax with small vs large catheters but these numbers are based on draining air not blood. Sample size analyses were conducted in PASS 13⁹.

Aim II

Calculations of sample size were based on two-group comparisons of empyema rates. With assumptions of empyema rate is 5% in the retrospective group and 2% in the prospective group, 586 patients in each group are needed to achieve a power of 0.8 with $\alpha=0.05$. To account for potential attrition, we will inflate the number of patients by 10% resulting in a total of 645 patients in the retrospective group and 645 patients in the prospective group. The sample size was calculated by using the PASS 15¹⁰.

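### Length of stay is to be compared by Poisson regression with no provision for overdispersion; if stay varies more than its mean, the standard error is too small and a 5% test too liberal.

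*Combined protocol and SAP*

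**What the plan says.** Section 9.4.3 gives the whole specification in one sentence: "Length of stay will be compared using Poisson regression with a main effect of group". The Statistical Analysis entry of the synopsis (Section 1.1) says the same. Section 3 lists the outcome under Aim I as "Endpoint IV: Length of hospitalization", one of nine secondary endpoints (II to X). The Schedule of Activities records it in days, next to ICU days and ventilation days.

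No section mentions overdispersion, a scale parameter, robust standard errors, a negative binomial model, or a check of the variance against the mean. The one sensitivity analysis that reaches the secondary outcomes (Section 9.4.1) adjusts for baseline imbalance. No mean, SD, alpha or sidedness is given for length of stay.

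Two statements on randomisation bear on the remedy. Section 6.4 has the allocation "stratified by location (Emergency Department and Surgical & Trauma ICU". The synopsis names no stratum: "Permuted block randomization with random block sizes to allocate patients in a 1:1 allocation to the 14 or 28 tube sizes".

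**The concern.** Poisson regression takes its standard error from the assumption that the variance equals the mean. If stays vary more than that, the standard error is too small, the confidence interval too narrow and the p-value too low, however well the group means are estimated.

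The population described makes equality implausible. Patients come from the emergency department and the ICU, some are ventilated, and Section 8.3.7 anticipates substantial trauma-related complications. Each of these spreads length of stay.

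At stake is a chance difference in stay between the tube sizes being reported as a real benefit or harm of the smaller tube. The primary comparison of drainage failure does not use this model.

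**Working it through.** **Inputs from the documents.** Section 9.2: "With a sample size of n=126 per group, we will have 80% power". Section 4.1 gives the matching total of 252, and Section 6.4 the 1:1 allocation. The model is the one in Section 9.4.3.

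**Inputs assumed.** A two-sided 5% test and a 95% interval for length of stay, and every mean, SD, ratio and location split below.

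**Step 1: the plan's own figure.** No calculation is given for length of stay, so the only figure to reproduce is the number per arm. With 7% failure in both arms, a margin of 8 points and one-sided alpha 0.05:

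n = (1.645 + 0.842)² × 2 × 0.07 × 0.93 / 0.08² = 125.8, rounded up to 126.

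This matches, so 126 per arm is used below.

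**Step 2: effect of overdispersion.** Let r = variance/mean of stay. The true standard error of the log ratio of means is √r times the Poisson one, so with no true difference

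actual size = 2 × [1 − Φ(1.96/√r)].

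The simulation column uses negative binomial stays with mean 8, 126 per arm and 20,000 trials.

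| r | √r (factor for interval width) | Size, formula | Size, simulated |
|---|---|---|---|
| 1.5 | 1.2 | 11.0% | 10.9% |
| 2 | 1.4 | 16.6% | 16.9% |
| 3 | 1.7 | 25.8% | 25.9% |
| 5 | 2.2 | 38.1% | 37.7% |
| 10 | 3.2 | 53.5% | 54.2% |

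At r = 1 the formula gives 5.0% and a simulation 5.1%. Coverage of a nominal 95% interval is one minus the size: 83.4% at r = 2 and 61.9% at r = 5. With a mean of 8 days, r exceeds 1 as soon as the SD exceeds √8 = 2.83 days.

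**Step 3: a more skewed shape.** Stays drawn from a rounded lognormal distribution, with r = SD²/mean:

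| Mean/SD | r | Ordinary Poisson |
|---|---|---|
| 5/3 | 1.8 | 14.5% |
| 5/4 | 3.2 | 27.0% |
| 8/6 | 4.5 | 35.4% |
| 10/10 | 10 | 52.5% |

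The formula gives 14.4%, 27.3%, 35.6% and 53.5%. The inflation therefore depends on r and hardly on the shape.

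**Step 4: candidate remedies, no stratification.**
- Robust standard errors: 5.3% throughout for the negative binomial stays of Step 2, and 5.3% to 5.8% for the skewed stays of Step 3.
- Pearson-scaled (quasi-Poisson) standard errors: 4.9% to 5.2% for r from 1 to 12, with negative binomial stays.
- Negative binomial regression: 4.7% to 5.7% when stays follow that model, but about 6% to 12% for the skewed stays.

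**Step 5: stratification by location.** Assume 60% and 40% of patients in two locations with mean stays of 5 and 12 days. The overall mean is 0.6 × 5 + 0.4 × 12 = 7.8, and the between-location variance is 0.6 × 0.4 × 7² = 11.76. If the ratio within each location is w, the overall ratio is r = (7.8w + 11.76)/7.8, which is 2.51, 3.51, 4.51 and 6.51 for w = 1, 2, 3 and 5.

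Without stratification, r governs. Ordinary Poisson was simulated at 21.7%, 29.1% and 36.5% for w = 1, 2 and 3.

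With stratification, location is balanced between arms and only w inflates the test. A robust error without a location term still carries r, so its size is 2 × [1 − Φ(1.96 × √(r/w))].

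| w | Ordinary Poisson, simulated | Robust, no location: formula | Robust, no location: simulated | Robust with location, simulated |
|---|---|---|---|---|
| 1 | 4.9% | 0.2% | 0.2% | 5.0% |
| 2 | 16.8% | 0.9% | 1.0% | 5.5% |
| 3 | 26.2% | 1.6% | 1.9% | 5.3% |
| 5 | 38.4% | 2.5% | 2.8% | 5.5% |

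Stratification removes the between-location part of the problem and no more. A robust error then needs the location term, or the test becomes too strict. (The last column used 3,000 trials.)

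**The case against.** The best defence has four parts.

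- **The plan is brief, not wrong.** Naming Poisson regression does not rule out a scaled or robust variance, and a competent analyst would check dispersion. That is true of practice, but the plan does not say it. Choosing the variance after seeing the data is what pre-specification is meant to prevent, and the sentence followed literally gives the ordinary standard error.
- **Every size is assumed.** The documents give no mean, SD or ICU share. No alpha is stated for this test, and the 95% intervals promised in Section 9.4.3 are for re-intervention and readmission. This stands. The omission and the direction of the error are firm; the amount, between 5% at a ratio of 1 and 54% at a ratio of 10, is not. The standard error is too small whatever alpha is used.
- **The choice of remedy is partly preference.** This also stands in part. A Pearson scale did as well as robust errors where both were simulated. The warning about negative binomial regression rests on one assumed skewed shape, and repeat runs put its lower end nearer 6% than 7%.
- **It is a secondary endpoint.** It is, and neither the sample size nor the conduct of the trial changes. That limits the weight of the point but does not remove it.

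The synopsis omits the stratum rather than denying it. The discrepancy matters here only because it decides whether the location term is needed.

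**Conclusion.** The concern holds. As written, the length-of-stay analysis has a standard error that is too small whenever stay varies more than its mean, which is very likely in a mixed emergency department and ICU trauma population. Assuming a two-sided 5% test, a ratio as modest as 2 more than triples the false-positive rate, to about 17%; a ratio of 5 takes it to about 38%. Under stratified allocation these ratios are those within location. If the ratio is 1, nothing is wrong. Correcting this is advisable before the analysis; nothing in the primary analysis needs to change because of it.

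**What to change.** In Section 9.4.3 and in the synopsis, specify Poisson regression with robust (sandwich) standard errors for length of stay, and state the alpha, sidedness and confidence level.

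Reconcile the randomisation entry of the synopsis with Section 6.4. If allocation is stratified by location, add location to the model: without it the robust test is conservative, with it the size is about 5%.

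A Pearson-scaled Poisson model is a reasonable alternative if named in advance. It would need the location term for the same reason; its size under stratified allocation was not simulated here. Negative binomial regression is also possible, but its model-based standard error is less safe if stays are more skewed than that model allows.

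The cost is wording and one line of code. Location is already known at randomisation, and no new data or patients are needed. Intervals for length of stay will be wider if stays are overdispersed, as they should be.

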6.2 INDEX HOSPITALIZATION REVIEW

At the time of enrollment, baseline demographic and injury characteristics will be recorded. Baseline data to be recorded include:

- Demographics (age, sex)
- Vital signs (pre- and post-tube insertion)
- Mechanism of injury (blunt vs penetrating)
- Radiographic findings (pneumothorax, hemothorax or hemopneumothorax)
- Initial laboratory values (hematologic panel, chemistry panel, coagulation panel, toxicology, blood gases)
- Calculated injury severity score

The day of tube insertion will mark study day 0. Subjects will be monitored daily by study staff in the form of chart review for the duration of their hospitalization. A daily data log will be kept for each patient/ The information to be recorded includes:

- Volume of hemo/hemopneumothorax drainage
- Tube misplacement
- Tube migration
- Presence of air leak
- Need for additional thoracostomy tubes

- Need for operative intervention (VATS, thoracotomy)
- Date and time of pneumo/hemo/hemopneumothorax resolution as confirmed by a radiologist
- Date and time of chest tube removal
- Recurrent pnemo/hemo/hemopneumothorax
- Development of infection

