8.3.7 SERIOUS ADVERSE EVENT REPORTING

Participants will be monitored for serious adverse events from the moment of randomization through 90 days post tube insertion. Due to their mechanism of injury and high trauma burden, participants are expected to have significant trauma related complications. AEs or SAEs determined to be unrelated to study procedure or tube size will not be reported to the IRB. Submission of any serious adverse event will not occur until relatedness of the event has been determined.

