9.4 STATISTICAL ANALYSES

9.4.1 GENERAL APPROACH

All analyses for this randomized trial will follow the intention to treat principle with an additional per protocol analysis given the non-inferiority hypothesis. We will first compare the baseline characteristics of the patients by group to assess for statistically significant or clinically meaningful imbalances. If either exists, these factors will be taken into account in sensitivity analyses for the primary and secondary outcomes.

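### Length of stay is modelled on tube group alone; prespecifying Injury Severity Score, mechanism and location, with a variance that allows overdispersion, would give a modestly sharper and validly reported estimate

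*Combined protocol and SAP*

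**What the plan says.** Length of stay is a secondary endpoint of Aim I, listed in section 3 as "Endpoint IV: Length of hospitalization". Its whole analysis is one sentence in section 9.4.3: "Length of stay will be compared using Poisson regression with a main effect of group". No covariate, stratification term or method of variance estimation is given.

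The next sentence of that section treats two other outcomes differently: "Post insertion pain and vital signs will be compared using analysis of covariance controlling for pre-procedural pain and vital signs".

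Section 6.2 lists the data recorded at enrolment, including "Calculated injury severity score" and mechanism of injury as blunt or penetrating. The Schedule of Activities (section 1.3) places the Injury Severity Score at screening, without the conditions attached to blood gases and toxicology. Section 6.4 stratifies randomisation by location: Emergency Department, or Surgical & Trauma ICU.

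Section 9.4.1 has a general rule. Baseline characteristics are compared between arms for statistically significant or clinically meaningful imbalance, and "If either exists, these factors will be taken into account in sensitivity analyses for the primary and secondary outcomes".

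**The concern.** Length of stay after trauma varies widely between patients, and overall injury severity and mechanism are plausible predictors of it. When such predictors are measured before treatment, putting them in the model removes part of the between-patient variation from the treatment comparison. This works whether or not the arms happen to be balanced.

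The imbalance rule in section 9.4.1 does not achieve this. If the arms are balanced on severity, no adjusted analysis of stay is planned. If they are not, the adjustment is chosen after seeing the data, under a trigger with no stated threshold, and it stays a sensitivity analysis. The stratification factor is also left out of the main model.

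What is at stake is efficiency on one secondary endpoint. The choice of variance matters too. A standard Poisson model fixes the variance at the mean, so any gain from covariates will not appear in its reported standard error.

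**Working it through.** **Inputs from the documents.** 252 patients are randomised 1:1, so 126 per arm (sections 4.1 and 9.2). The length-of-stay model has group only (9.4.3). Injury Severity Score and mechanism are baseline data (6.2).

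**Assumptions, not in the documents.** Mean stay is 10 days. The coefficient of variation (CV) of patients' expected stay is 0.5 to 1.0. The share *s* of between-patient log-variance explained by Injury Severity Score and mechanism is 10%, 20% or 30%. Expected stays are log-normal, observed days are Poisson around them, and there is no true group effect.

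**Step 1: the plan's own figure.** No precision figure is given for length of stay. The Aim I sample size reproduces with 7% failure in both arms, a margin of 8 points, one-sided 0.05 and 80% power:

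(1.645 + 0.842)² × 2 × 0.07 × 0.93 / 0.08² = 125.8, so 126 per group.

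It depends only on the primary outcome, so the length-of-stay model does not affect it.

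**Step 2: standard error reported by a plain Poisson model.** For the log ratio of mean stay this is √(2/(126 × 10)) = 0.040. It depends on total days only, so it is the same with or without covariates.

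**Step 3: true standard error, group-only model.** √[(2/126) × (1/10 + CV²)]:
- CV 0.5: √(0.01587 × 0.35) = 0.075
- CV 0.8: √(0.01587 × 0.74) = 0.108
- CV 1.0: √(0.01587 × 1.10) = 0.132

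The plain Poisson standard error is therefore about one half (0.040/0.075) to one third (0.040/0.132) of the true one.

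**Step 4: true standard error after adjustment.** Under the same assumptions the large-sample ratio of adjusted to unadjusted standard error is

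√{[0.1 + (1 + CV²) − (1 + CV²)^s] / [0.1 + CV²]}.

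Example, CV 1.0 and s = 0.2: √[(0.1 + 2 − 1.149)/1.1] = √0.865 = 0.930, a 7.0% reduction.

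| Share explained | Formula, CV 0.5 / 0.8 / 1.0 | Range including simulations |
|---|---|---|
| 10% | 3.3% / 3.5% / 3.3% | 2-4% |
| 20% | 6.7% / 7.3% / 7.0% | 6-8% |
| 30% | 10.4% / 11.5% / 11.1% | 8-13% |

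The simulations used 126 per arm and the same assumed values. They scatter around the formula, which is why the last column is wider.

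Since sample size scales as 1/(SE ratio)², the 20% row is worth between 252/0.94² = 285 and 252/0.92² = 298 patients in place of 252.

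**Step 5: why the variance must change too.** In simulation with no group effect, the two-sided 5% test using the plain Poisson standard error rejected 29% to 55% of the time unadjusted. With the covariates added, and up to 50% of log-variance explained, it still rejected 20% to 54%. With a robust variance, rejection was about 5% to 6% in both models.

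**The case against.** **Randomisation makes the group-only comparison unbiased, and this is one of nine Aim I secondary endpoints.** Both statements are true. They limit the importance of the point to efficiency and do not remove it.

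**Section 9.4.1 already provides for adjustment.** A reader might infer from 9.4.3 alone that stay can never be adjusted, which is wrong. The provision depends on observed imbalance and is confined to sensitivity analyses, so it does not replace a prespecified main model.

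**Covariates alone do not repair the planned sentence.** This objection stands. One might infer that the planned test would mainly miss real differences. With plain Poisson standard errors and overdispersed stays, the nearer danger is false positives. The precision gain in the estimate is real, but it reaches the reported interval only with a suitable variance, so the fix must include one.

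**The gain is assumed.** This also stands. The familiar factor √(1 − R²) would suggest reductions of 5%, 11% and 16% at 10%, 20% and 30% explained, with 20% equivalent to a quarter more patients. That is a linear-model result for the share of total variance. For the share of between-patient log-variance in this model, the reductions are smaller.

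**Other inferences that go too far.** Section 8.3.7 says "Due to their mechanism of injury and high trauma burden, participants are expected to have significant trauma related complications". A reader might take this to mean that the plan expects other injuries to dominate length of stay. The sentence concerns safety reporting and says nothing about stay or what drives it. Nor is the treatment of pain and vital signs an inconsistency: they are adjusted for their own pre-insertion values, and length of stay has none. Finally, one might infer that ICU days before the tube are counted. The documents do not say when the count starts, so this is conjecture.

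**Conclusion.** The point holds as a modest, inexpensive improvement to one secondary analysis. The main length-of-stay model omits two baseline covariates that the trial collects and the factor used to stratify randomisation, and section 9.4.1 does not fill the gap. The estimate is unbiased but less precise than it could be.

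Under the assumed mean of 10 days and CV of 0.5 to 1.0, the true standard error would fall by about 2-4%, 6-8% or 8-13% for 10%, 20% or 30% of between-patient log-variance explained. The share is an assumption, and the gain could be trivial if it is small. Location was not in the calculation, so any contribution from it is not counted.

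The direction does not depend on the assumed values, provided the covariates are prognostic. With a log link, adjustment leaves the group ratio as the same quantity. The need for an overdispersion-tolerant variance follows from stays varying more than a Poisson count would, which is assumed here because the documents give no variance. The primary analysis and the sample size of 126 per group are unaffected.

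**What to change.** In section 9.4.3 and the matching synopsis text, state that:

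1. the main length-of-stay model includes tube group, Injury Severity Score, mechanism (blunt or penetrating) and randomisation location, fixed in advance whatever the observed balance; and
2. inference uses a robust (sandwich) variance with the Poisson model, or a quasi-Poisson or negative binomial model.

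The group-only model can be kept as a supporting analysis with the same kind of variance.

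The cost is a line or two of text. The covariates and location are already recorded, no new data are needed, and the sample size does not change.

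Stating that stay is counted from tube insertion (day 0 in section 6.2) is a separate, optional clarification. It defines the endpoint and is not part of the precision argument.
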